#### 4. *Approach*

- a. Study design

i. This will be a prospective randomized controlled trial at Regions Hospital in Saint Paul, MN and Hennepin County Medical Center in Minneapolis, MN to compare primary outcomes of subjects between audio distraction groups during traction pin placement. This study will also include a cross-sectional descriptive element by examining above listed secondary outcome measures. It will explore if either of these outcomes are different between the two subject groups in an exploratory fashion.

Group selection was randomized through Microsoft Excel 2010, of which subjects are split into blocks of 10, with each block held at a fix ratio of 0.5 for audio distraction and without audio distraction.

i. Inclusion

1. >18 years old
2. Conscious, oriented, able to give informed consent
3. Medical need for distal femoral or proximal tibial skeletal traction pin placement

ii. Exclusion

1. Medical contraindication to skeletal traction
2. Endotracheal intubation
3. Unable to participate in verbal communication throughout the procedure and in the recovery phase
4. Sensory impairment to pain
5. Inability to make accurate mark on VAS 2/2 cognitive, motor or visual deficiencies.

b. Data collection process

- i. Identify patients at Regions Hospital who meet inclusion criteria who are determined to need skeletal traction pin placement
  1. Patients meeting inclusion criteria will be identified by the on call junior residents at Regions Hospital and Hennepin County Medical Center
- ii. Recruitment of patients for inclusion in this study will be complete by the orthopedic resident placing the skeletal traction pin. Patients will be recruited for inclusion in this study after determining the medical need for placement of a skeletal traction pin.
- iii. Consent
  1. Written informed consent will be obtained by the orthopedic resident performing traction pin placement prior to initiating steps for traction pin placement
  2. Patients will acknowledge that the study has been explained adequately and that they are free to withdraw from study at any time without effect on their treatment and management
  3. Patients will provide consent for participation in this study at the time of consenting for placement of the skeletal traction pin. Minors do not meet inclusion criteria for this study.

iv. Data sources needed for this study

1. Chart review for current injury, date and time of injury, and medications given during hospital visit.

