2. Chart Review for patient age, gender, height and weight
3. Survey for patient
  - a. Visual analog scale (VAS) to rate pain
  - b. Visual analog scale (VAS) to rate anxiety
  - c. Visual analog scale (VAS) to rate overall patient experience
4. Survey for resident
  - a. Cooperation of patient on 1-10 scale; fully cooperative to combative
  - b. Ease of procedure on 1-10 scale; easy to most difficult
5. Overall time required for placement of skeletal traction pin

v. Process steps for data acquisition

1. Demographic data (age, sex, injury, date/time of injury)- completed by patient; obtained by resident, and/or retrospective chart review by the research assistant.
2. Time of procedure from injection of lidocaine to completion (disconnecting drill); obtained by resident
  - a. Start time just prior to lidocaine injection
  - b. Stop time after drill disconnected from pin
3. Medications given during procedure; obtained via retrospective chart review by research assistant
4. Post-procedure VAS pain, anxiety, and experience surveys completed by patient, obtained by resident immediately after hanging of traction weight.
5. Post-procedure patient compliance and ease of procedure surveys completed by the resident after completion of procedure

c. Intervention, treatments

- i. Standard of care will be provided by the orthopedic resident for skeletal traction pin placement. Those included in this study and randomized into the treatment arm will be given an mp3 device to listen to genera of music of their choosing in addition to be treated to the current standard of care. Those randomized into the control arm will be treated to the current standard of care
- ii. Patients will be randomized by the orthopedic resident into 2 groups; Audio distraction with music versus control group with no music. This will be done by sealed envelopes drawn after consent for the procedure.

d. *Outcomes/endpoint and other variable definitions, and instruments used*

- i. A 10-point visual analog scale for patient experience (1 worst possible experience, 10 best possible experience)
  1. Singer 1998; Results suggested that the satisfaction VAS is both reliable and valid.

- ii. A 10-point visual analog scale for pain (1 no pain, 10 worst pain)
  - 1. Bijur 2001; Results demonstrated that the VAS is sufficiently reliable to be used to assess acute pain
  - 2. Todd 1996; demonstrated the validity of the VAS for acute pain measurement among ED patients to measure acute pain

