**6. Risks and Benefits**

- a. Potential risk factors with audio distraction group
  - i. Patient may not hear resident when attempting to communicate
    1. Resident will be able to communicate with an assistant in the room to get the attention of the patient, if needed.
  - ii. Patient may receive less pain management with the assumption they will have higher pain tolerance from the audio distraction
    1. Resident will continue to follow standard of care for traction pin placement
  - iii. Benefit for patient in audio distraction group to experience less discomfort during traction pin placement

- iv. Benefit to society, as this study may provide an opportunity for providers to decrease the level of discomfort in patients who need traction pin placement.

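### All three primary ratings are handed back to an unblinded resident whose own care is being rated; a patient-sealed form would cheaply reduce the courtesy bias this invites

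*Combined protocol and SAP*

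**What the plan says.** Section 2 makes overall experience, anxiety and pain the three primary aims. All are visual analogue scales marked by the patient. Under 4. Approach, b.v item 4, the patient fills in the forms and they are "obtained by resident immediately after hanging of traction weight".

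The other steps of the trial also fall to the resident:

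- Recruitment (b.ii) is "complete by the orthopedic resident placing the skeletal traction pin".
- Consent (b.iii.1): "Written informed consent will be obtained by the orthopedic resident performing traction pin placement".
- Allocation (c.ii): "Patients will be randomized by the orthopedic resident into 2 groups; Audio distraction with music versus control group with no music". The resident does this with sealed envelopes, after consent.
- Procedure (c.i): "Standard of care will be provided by the orthopedic resident for skeletal traction pin placement".

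The research assistant is named only for chart review. Nothing is said about blinding, private completion or sealed return of the form. The limitations list recall bias for pain and for procedural difficulty, but not lack of blinding or courtesy toward the person collecting the rating.

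**The concern.** Each primary outcome is subjective, and none is objective enough to check the others against. The experience scale in particular comes close to a rating of the person who collects it. A patient who expects that person to see the answer may rate more kindly.

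This matters most if the kindness differs by arm. Both parties know the allocation: one patient received music, while the other agreed to a music trial and received none. Such a shift arises after randomisation, so randomisation does not remove it. The planned t-tests and the regressions with demographic covariates cannot separate it from a treatment effect. The cited reliability studies of the scales do not address who should receive the completed form.

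**Working it through.** **1. What is stated and what is inferred.** It is stated that the patient marks the scales, that a resident obtains the forms straight after the weight is hung, and that the resident placing the pin recruits and consents. Allocation and the procedure are assigned to the orthopaedic resident. Two things are inferred. The first is that the collector is that same resident; item 4 says only resident, but no other resident is given the task. The second is that the form changes hands at the bedside, which follows from the timing. Both are the natural reading, but neither is written down.

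**2. The plan's own figures.** The power statement gives a difference of 2.0, SD 2, alpha 0.05, 80% power and 21 per group (42 in total). Sidedness of the test is not stated; two-sided is assumed here.

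n per arm = 2 × (z₀.₉₇₅ + z₀.₈₀)² × (SD/difference)² = 2 × (1.960 + 0.842)² × (2/2)² = 15.7, so 16 by the normal approximation and 17 by the t-test.

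The stated 21 is not reproduced; 21 per arm gives 88.5% power by the t-test. That is a separate matter and neither supports nor weakens this point. The 21 is used below because it is the planned size.

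**3. A shift that differs by arm.** Let b be the between-arm difference produced by reporting alone, with no true effect.

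- Standard error of the difference = 2 × √(2/21) = 0.617
- Degrees of freedom = 40; two-sided 5% critical value = 2.021
- Smallest significant observed difference = 2.021 × 0.617 = 1.25 points
- Noncentrality = b / 0.617; the rejection rate comes from the noncentral t distribution

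| Assumed b (points) | Noncentrality | Rejection rate per outcome |
|---|---|---|
| 0 | 0 | 5.0% |
| 0.25 | 0.405 | 6.8% |
| 0.5 | 0.810 | 12.4% |
| 0.75 | 1.215 | 22.0% |
| 1.0 | 1.620 | 35.3% |

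Every b is assumed; the documents give none. The 1.0-point row is half the planned effect and should be read as an upper illustration, not as a small shift.

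**4. Courtesy equal in both arms.** If every patient shifts by c, the difference is (μ₁ + c) − (μ₂ + c) = μ₁ − μ₂, and the false-positive rate stays at 5%. If courtesy instead compresses scores, so that a true 2.0 is seen as 1.5 with SD still 2, power falls from 88.5% to 66.0%. The size of that compression is again assumed.

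**The case against.** The strongest reply is that the patient, not the resident, marks the scale, and that immediate completion limits the recall bias the protocol worries about. Both are true. The resident does not score the outcome, so the route is deference or prompting, and the immediate time point should be kept.

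A reader might infer more than the documents support:

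- **That the handover is face to face and the resident reads the answers.** The documents do not say how the form is returned or whether it is looked at.
- **That the resident gives the patient the music, so gratitude favours that arm.** Section c.i uses the passive and names no giver. Courtesy toward the resident can operate in both arms. A difference between arms is plausible because allocation is known, but it is not documented.
- **That the rejection rates estimate the damage, or what an envelope would remove.** They would follow from any bias of the assumed size. Patients know whether they heard music, so expectation bias persists whoever collects the form, and the collector's share cannot be separated from it.
- **That an independent collector is already in place.** Section 6, a.i.1 says "Resident will be able to communicate with an assistant in the room to get the attention of the patient, if needed". This is a safeguard against the headphones blocking communication. It gives the assistant no study duty and does not say that the assistant stays until the forms are marked.

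Sealing the form also has a real cost: nobody checks it at the bedside. The experience scale runs opposite to the other two (10 is best for experience, worst for pain and anxiety), the acute setting is already listed as limiting survey information, and the plan describes no handling of missing scores.

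These replies limit the size and certainty of the point. They do not supply a reason for returning an open form to the treating resident.

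**Conclusion.** The point holds as a weakness in how the primary outcomes are collected, not as a demonstrated bias. As written, the pain, anxiety and experience forms appear to go back to an unblinded person whose care they rate, with no privacy safeguard and no mention in the limitations. Neither size nor direction can be determined from the documents. Under the assumptions above, the false-positive rate per outcome would rise from 5% to between 6.8% and 35.3% for an arm-dependent shift of 0.25 to 1.0 points. The conclusion rests on the natural reading that the collecting resident is the treating one. It is best classed as a cheap improvement: only part of the open-label bias can be removed, but that part can be addressed at very little cost.

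**What to change.** Replace the collection step in b.v item 4 with the following, identical in both arms and at the present time point:

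- The patient marks the three scales without the resident looking, puts the form in an envelope and seals it.
- The form states that the treating team will not see the answers and asks the patient to mark all three lines.
- Anyone present may pass on the sealed envelope. It is opened only at data entry, by existing study staff not involved in the procedure.

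Add lack of blinding to the limitations, noting that expectation bias remains.

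The cost is envelopes, a short protocol change and a small added duty for existing study staff, whose availability at both hospitals should be confirmed. Sample size, timing and analysis are unchanged. The downside is the loss of any bedside check for blanks or for misreading of the reversed experience scale. The printed request to mark all three lines reduces the risk of blanks, and clearly labelled scale ends would help with the reversal.

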### **2. Study aims:**

- a. Primary:
  - i. To determine if audio distraction will improve subject's overall experience during skeletal traction pin placement compared to those without audio distraction.
  - ii. To determine if subject anxiety decreases with the use of audio distraction compared to those without audio distraction during skeletal traction pin placement
  - iii. To determine if subject pain decreases with the use of audio distraction compared to those without audio distraction during skeletal traction pin placement
  
- b. Secondary:
  - i. To determine if audio distraction changes provider perception of procedure difficulty
  - ii. To determine if audio distraction changes overall skeletal traction pin placement procedure time
  - iii. To determine if pain medicine use is different in patients who have audio distraction compared to those without audio distraction during skeletal traction pin placement.

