- iii. A 10-point visual analog scale for anxiety (1 no anxiety, 10 worst anxiety)
  - 1. Hornblow 1976; Results suggest that VAS is sufficiently reliable to be used to assess acute pain.
- iv. Pain medication used pre/post traction pin placement
- v. Overall time required for placement of skeletal traction pin
- vi. Resident perception of procedural difficulty
- vii. Intermediary Newman-Keuls (SNK) analysis techniques will be utilized to regularly perform preliminary *post-hoc* tests. This will aid towards

*statistical analysis plan*

- i. T-Test of Sampling Demographic Data
- ii. T-test of Primary Outcome Measures between subject groups
  - 1. Pain Survey Scores
  - 2. Anxiety Survey Scores
  - 3. Experience Survey Scores
- iii. Linear & Logistic Regression Analysis of Primary Outcomes
  - 1. Addition of Demographic Covariates
  - 2. Observing both Linear & Non-Linear identities of the relationship.
- iv. T-Test of Secondary Outcome Measures between subject groups
  - 1. Perception of Difficulty
  - 2. Procedural Time
  - 3. Pain Medication
- v. Linear & Logistic Regression Analysis of Secondary Outcomes
  - 1. Addition of Demographic Covariates
  - 2. Observing both Linear & Non-Linear identities of the relationship
- vi. Power analysis or statement of precision

A power analysis was performed to estimate the minimum sample size needed to adequately detect a clinically significant change in anxiety and pain scores between the audio distraction groups. At a Type I error rate of 0.05 ( $\alpha=0.05$ ) and 80% power ( $\beta=0.80$ ), the power analysis identifies a minimum sample size of 42 total participants, 21 for each group. The estimated effect size is 2.0 on the utilized 10-point scale with a two-sided standard deviation of two. These measures for effect size are adopted from a previously performed colonoscopy audio distraction study which identified clinically significant results (Costa 2010). A power analysis for secondary outcome measures was not performed due to their non-inferential nature.
- vii. *Strengths*

1. Regions Hospital and Hennepin County Medical Center provides sufficient access to the study population and the facility is adequate to conduct the study. Both Level I Trauma centers.
2. Adequate qualified staff members to conduct the study
3. Staff will be adequately trained on the protocol and their specific research related duties.
4. Exhaustive primary & secondary outcome assessment.
5. Use of verified survey techniques.

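### The pain-medicine outcome is defined over one period and collected over another, and analgesia is not planned or time-stamped before the treating resident learns the arm

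*Combined protocol and SAP*

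**What the plan says.** On allocation and care, Section 4.b.iii has the resident who will place the pin obtain consent before any placement step. Section 4.c.ii has the orthopedic resident randomize: "This will be done by sealed envelopes drawn after consent for the procedure". Section 4.c.i has the resident provide the standard of care, with music added in one arm. Section 6.a.ii recognises that music patients might be given less pain management because they are assumed to tolerate more. The stated answer is that the resident keeps to standard of care. No section says what that is for analgesia.

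On times, Sections 4.b.iv and 4.b.v list the time of injury, a start time just before lidocaine and a stop time when the drill is disconnected. The pain, anxiety and experience VAS forms come later, immediately after the traction weight is hung. Neither the envelope time nor the time of VAS completion is listed.

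On the medicine outcome:
- Section 4.d.iv, among the outcome and variable definitions: "Pain medication used pre/post traction pin placement".
- Section 4.b.v item 3, the collection step: "Medications given during procedure; obtained via retrospective chart review by research assistant".
- Section 4.b.iv item 1, a chart-review data source: "medications given during hospital visit".
- Secondary aim iii asks whether "pain medicine use is different in patients who have audio distraction compared to those without audio distraction during skeletal traction pin placement".

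The analysis plan (item iv) has a "T-Test of Secondary Outcome Measures between subject groups", with pain medication named as one of the measures, and item v adds regression with demographic covariates. On status, item vi states: "A power analysis for secondary outcome measures was not performed due to their non-inferential nature".

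**The concern.** There are two linked gaps.

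First, the outcome definition and the collection step do not describe the same drugs. An analyst following Section 4.d.iv would count medicine before and after placement. One following Section 4.b.v would count medicine during it. The *pre* part can include drugs given before the envelope was opened, which music cannot have influenced. The t-test line does not say which period is used, whether *pre* and *post* are compared separately, when *post* ends, or in what unit different drugs are combined.

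Second, the plan foresees that knowing the arm might change how much analgesia is given, yet it collects nothing that would show whether this happened. If music patients were offered less, their pain scores would tend to rise and a true benefit on the pain aim could be hidden. The same shift would appear under secondary aim iii as a medicine saving. Neither the envelope time nor the resident's prior intention can be reliably recovered from a later chart review.

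**Working it through.** The point rests on reading the text. The plan's only computed figure, 42 participants, concerns the pain and anxiety scores and plays no part here.

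1. **Order of events.** Consent precedes all placement steps (4.b.iii) and the envelope follows consent (4.c.ii). Music must be running during insertion, so the natural reading is that the resident knows the arm before lidocaine, though no section says so outright. Any premedication chosen between envelope and lidocaine is chosen with the arm known.

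2. **What the recorded times can separate.** The earliest procedural time is just before lidocaine. A drug given after the envelope but before lidocaine falls outside the timed procedure and could be filed under *pre*, although it was given after allocation. Without an envelope time it cannot be told apart from a drug given before allocation.

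3. **Definition against collection.**
   - Definition (4.d.iv): *pre* and *post*, with no start or end. The *pre* part mixes drugs from before and after allocation.
   - Collection (4.b.v item 3): *during* the procedure, which appears to fall after allocation.
   - Data source (4.b.iv item 1): the hospital visit. This says what will be looked up, not what will be analysed. It does mean that earlier medicine is already available for use as a covariate.

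4. **What drugs given before allocation do to the comparison.** Under randomization their expected difference between arms is zero, so the expected difference in the total is unchanged and only its variance grows. Suppose medicine given before allocation is independent of later medicine and has r times its variance. The standardized difference is then multiplied by 1/√(1 + r). The documents give no r, so these are assumed values:
   - r = 0.5: 1/√1.5 = 0.82
   - r = 1: 1/√2 = 0.71
   - r = 2: 1/√3 = 0.58

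   A positive correlation between earlier and later medicine would dilute more, and a negative one less. These factors illustrate dilution and do not estimate it for this trial.

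5. **Where the outcome window should end.** The pain VAS follows hanging of the weight, after drill disconnection. A window closed at the existing stop time would miss medicine given between the two, which can affect the score. The window should therefore run to completion of the VAS.

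6. **Direction of any arm-driven change in analgesia.** Less analgesia with music means higher pain scores with music, which works against a pain benefit and towards an apparent medicine saving. The documents give no frequency or dose from which to size either effect.

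**The case against.** The strongest reply is that both arms are promised the same standard of care, that Section 6 anticipates the risk, that the strengths list says "Staff will be adequately trained on the protocol and their specific research related duties", and that the limitations mention an attempt at a standardized procedure. Knowledge of the arm is unavoidable with headphones. The documents do not say who orders systemic analgesics, so the resident's influence on total medicine is partly inferred. The start time just before lidocaine already gives a workable lower limit for medicine during the procedure, and the outcome is exploratory.

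Much of this stands, and it limits the point. Training and a common standard make the risk less likely, but they leave no record of what was intended or when the arm became known. The lidocaine time misses premedication given after the envelope, which is where knowledge of the arm could act.

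A reader might also infer more than the text supports:
- **That three outcome windows conflict.** The hospital-visit wording is a data source. In secondary aim iii the closing phrase may qualify the audio distraction rather than the medicine use; the anxiety and pain aims end in the same way. The clear conflict is one definition against one collection step.
- **That drugs given before allocation bias the comparison.** They balance on average; the cost is noise.
- **That open allocation is itself the defect, or that less analgesia would produce a false pain benefit.** The first is inherent in the intervention. The second has the direction wrong.
- **That the harm can be stated as lost power for the pain score.** Such a figure would describe the slack in 21 per arm under an assumed shift. It would not measure this gap.

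**Conclusion.** The point holds, at minor to moderate priority. The definition in Section 4.d.iv and the collection step in Section 4.b.v disagree, and the *pre* part can bring in drugs that music could not affect. The consequence is dilution of one exploratory comparison and uncertainty about what was compared, not bias. Separately, the plan names under-treatment in the music arm as a risk but neither records the intended analgesia before allocation nor keeps an allocation time, so its occurrence could not be checked. If it occurred, it could hide a true pain benefit and pass for a medicine saving.

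No size is claimed for either effect. The conclusion assumes that the envelope is opened before lidocaine and that the resident has at least some influence on analgesia. The first is the natural reading; the second is not fully settled by the documents.

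**What to change.** 1. **Section 4.c.ii.** After consent, the resident writes the planned usual-care analgesia, then opens the envelope and records the time. Later changes are allowed for clinical need, with the reason noted.
2. **Sections 4.d.iv and 4.b.v item 3, and the analysis plan.** Define one outcome: pain medicine given from the envelope time to completion of the post-procedure VAS, in a single stated dose unit. State whether lidocaine counts. Note the time on the VAS form, since it is not now collected.
3. **Analysis plan item v.** Use pain medicine given before the envelope time, from the chart review already planned, as a baseline covariate in the regression and not as part of the outcome.
4. **Reporting.** Give any later *post* medicine separately with a stated end time. List departures from the recorded plan by arm, with direction and reason, as description only.

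The cost is about a minute before allocation, one added line on the resident's form, a time on the VAS form, and some protocol wording. No extra patients or staff are needed, and no patient's treatment is restricted. Residual open-label bias remains: the resident still knows the arm and writes the reasons, so lower need cannot be fully separated from lower offering.

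### Three unranked primary outcomes are each t-tested at 0.05 with no multiplicity rule, so the chance of at least one false-positive primary result is up to 14.3%, not 5%

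*Combined protocol and SAP*

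**What the plan says.** - **Aims (Section 2.a).** Three primary aims are listed without ranking. The first is "To determine if audio distraction will improve subject's overall experience during skeletal traction pin placement"; the other two are lower anxiety and lower pain.
- **Primary analysis (Section 4, statistical analysis plan, item ii).** "T-test of Primary Outcome Measures between subject groups", with the pain, anxiety and experience scores listed beneath it.
- **Further analysis of the same scores (item iii).** "Linear & Logistic Regression Analysis of Primary Outcomes", adding demographic covariates. Its role relative to the t-tests is not stated.
- **Power (item vi).** Type I error 0.05, 80% power, difference 2.0, SD 2, 42 patients (21 per group). The stated purpose is to "adequately detect a clinically significant change in anxiety and pain scores between the audio distraction groups". Experience is not named. The only mention of sidedness is attached to the SD: "with a two-sided standard deviation of two".
- **Multiple-comparison method (Section 4.d, item vii).** "Intermediary Newman-Keuls (SNK) analysis techniques will be utilized to regularly perform preliminary" post-hoc tests. The sentence after it breaks off in the available text.
- **Timing (Section 4.b.v, item 4).** "Post-procedure VAS pain, anxiety, and experience surveys completed by patient, obtained by resident immediately after hanging of traction weight".

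Item vi calls only the secondary outcomes non-inferential. The three primary outcomes are therefore the confirmatory set.

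**The concern.** A 5% error rate for one test does not carry over to a set of three. If any of the three t-tests gives p < 0.05, nothing in the plan prevents that result from being reported as a positive primary finding, whichever outcome it is and whatever the other two show. The stated 0.05 then holds outcome by outcome but not for the trial's primary conclusion. Section 9 anticipates that the results could alter practice at one of the hospitals, so what counts as a positive trial should be fixed in advance.

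Three smaller gaps widen the choice: the tests' sidedness is not stated, the regressions on the same scores have no declared role, and the first-listed primary aim is outside the power statement.

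**Working it through.** **Inputs from the documents.** Three primary outcomes (Section 2.a); one t-test each (item ii); level 0.05, 80% power, difference 2.0, SD 2, 21 per arm (item vi); two arms allocated 1:1 (Section 4.a and 4.c).

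**Assumptions.** Each test uses 0.05, the only level given. Tests are two-sided unless noted. Scores are normal with equal pairwise correlations, and scales are aligned so that higher is better (experience runs the opposite way to pain and anxiety). The documents give no correlation, so a range is shown.

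**Step 1: the plan's own figure.** By normal approximation, n per arm = 2 × (1.960 + 0.842)² × (2/2)² = 15.7, so 16. The t-based calculation gives 16.7, so 17 per arm (34 in total). The stated 42 is not reproduced: with 21 per arm the t-test has 88.5% power, not 80%. That is a separate matter, and the error rates below do not depend on it, but it explains why 88.5% is the baseline used here.

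**Step 2: independent scores.**
- At least one false positive, either direction: 1 − 0.95³ = 1 − 0.8574 = 0.1426, or 14.3%.
- At least one false benefit, two-sided tests: 1 − 0.975³ = 1 − 0.9269 = 0.0731, or 7.3%.

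**Step 3: correlated scores.** Simulation of three t-tests, 21 per arm, no true effect, 400,000 trials per setting:

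| Correlation | 0 | 0.3 | 0.5 | 0.7 | 0.8 | 0.9 |
|---|---|---|---|---|---|---|
| Any false positive, two-sided 0.05 | 14.2% | 13.6% | 12.6% | 11.0% | 9.9% | 8.4% |
| False benefit, two-sided 0.05 | 7.3% | 6.8% | 6.3% | 5.5% | 5.0% | 4.2% |
| False benefit, one-sided 0.05 | 14.2% | 13.0% | 11.9% | 10.4% | 9.3% | 8.0% |
| Any false positive, Holm at two-sided 0.05 | 4.9% | 4.7% | 4.5% | 4.0% | 3.6% | 3.1% |

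The single-test benchmarks are 5% for the first and third rows and 2.5% for the second. The 14.2% at zero correlation agrees with the exact 14.26% within simulation error. A separate run that included negative correlations down to −0.49 found no either-direction rate above the one at zero.

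**Step 4: does Newman-Keuls cover this?** No. It compares several group means on one outcome. With two arms there is one comparison per outcome, so it has nothing to adjust across three outcomes.

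**Step 5: power under Holm.** The smallest p-value is compared with 0.05/3 = 0.0167, the next with 0.05/2 = 0.025, and the largest with 0.05. With a standardised effect of 2/2 = 1:
- All three effects real, 21 per arm: power per outcome 85.9% at correlation 0, falling to 81.8% at 0.9.
- One effect real, 21 per arm: 76.7% (noncentral t at 0.0167), against 88.5% at 0.05.
- One effect real, more patients: 79.1% with 22 per arm, 81.2% with 23 per arm.

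**The case against.** **The headline rate is a ceiling.** 14.3% needs independent scores, and three scales marked by one patient at one time are probably correlated. It also counts false harm, although the aims are directional. Both points are fair: at correlations of 0.7 to 0.9 the either-direction rate is 11.0% to 8.4%, and false benefit is 5.5% to 4.2%. Even so, every value exceeds its single-test benchmark of 5% or 2.5%.

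**Testing each outcome at 0.05 is inferred.** Item ii gives no level. Moreover, 21 per arm matches an adjusted level of 0.05/3 by normal approximation, and 0.05/2 by t-test, at 80% power. The sponsor should be asked how 42 was derived. However, item vi states 0.05 and mentions no adjustment, and a sample size is not a decision rule.

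**The text breaks off after the Newman-Keuls sentence.** The statement that no rule exists is therefore limited to the readable text. The method named there could not supply the missing control in any case.

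**Three aims may be three questions.** Some statisticians accept 0.05 per outcome when each aim is reported separately. That position is tenable if the plan states it. This plan neither states it nor says what a positive trial is.

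**The power figures rest on inputs for anxiety and pain.** This stands. Applying a difference of 2 and SD of 2 to experience is an assumption that the documents do not support.

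**Conclusion.** The concern holds and should be fixed. As written, the plan does not hold the error rate of its primary set at 0.05. In either direction, the chance of at least one false-positive primary result is at most 14.3%, and about 8% to 14% for correlations between 0.9 and 0. False benefit from two-sided tests is 4.2% to 7.3%, against 2.5%. If the tests are one-sided at 0.05, it is 8.0% to 14.2%, against 5%.

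These figures assume no true effect on any outcome, 0.05 for each test, normal scores, equal correlations and one final analysis. They leave out the repeated preliminary tests and the item iii regressions, which could raise the rate. Sidedness, the role of the regressions and the missing power for experience are lesser drafting points, best settled in the same edit.

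**What to change.** In item ii of the statistical analysis plan, choose one of the following.

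1. **Keep three primaries.** State that the tests are two-sided, apply Holm's procedure to pain, anxiety and experience at family-wise 0.05, and claim benefit only for outcomes that pass. With 42 patients this gives about 82–86% power per outcome if all three have the planned effect, but 76.7% for a lone effect, below the plan's 80% target. Restoring 80% for a lone effect takes 23 per arm: 46 in total, 4 more than planned.
2. **Name one primary.** Make the other two secondary. The test stays at 0.05, and power under the planning inputs stays at 88.5% with 42 patients. If experience is chosen, its own planning difference and SD are needed, because the present inputs were set for anxiety and pain.

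In either case, state that the item ii t-tests decide the primary conclusion and that the item iii regressions are supportive. In item vi, state that the power analysis covers anxiety and pain only and that experience was not separately powered.

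The cost is wording, apart from the optional 4 patients under the first choice.
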